APPENDIX 2. POTENTIALLY CLINICALLY SIGNIFICANT GUIDELINES

Criteria for identifying abnormalities as potentially CS are based on the Guidelines for the Division of Neuropharmacological Drug Products, US Food and Drug Administration (revised on April 2, 1987). The laboratory values identified below are not inclusive of all the safety laboratory analytes that will be assessed during this clinical trial. Safety laboratory analytes which are known to be elevated in some adults with Pompe disease (eg, AST, ALT, LDH) and safety laboratory analytes which are not listed below will be reviewed to determine if they are to be noted as potentially CS based on the magnitude of the out of range value as compared to the normal range and the subject's baseline value, and whether the out of range value is coded as CS by the principal investigator.

Laboratory Values		
Variable	Criterion Values	
	Standard Units	SI Units
Chemistry		
SGOT (AST)	$\geq 3 \times$ Upper Limit Normal	
SGPT (ALT)	$\geq 3 \times$ Upper Limit Normal	
Alkaline Phosphatase	$\geq 3 \times$ Upper Limit Normal	
LDH	$\geq 3 \times$ Upper Limit Normal	
BUN	≥ 30 mg/dL	≥ 10.7 μ M
Creatinine	≥ 2.0 mg/dL	≥ 176.8 μ M
Uric Acid	Male ≥ 10.5 mg/dL	≥ 624.6 μ M
	Female ≥ 8.5 mg/dL	≥ 505.6 μ M
Bilirubin (Total)	≥ 2.0 mg/dL	≥ 34.2 μ M
Hematology		
Hematocrit	Male $\leq 37\%$	
	Female $\leq 32\%$	
Hemoglobin	Male ≤ 11.5 g/dL	
	Female ≤ 9.5 g/dL	
Platelets	$\leq 75,000/\text{mm}^3$ or $\geq 700,000/\text{mm}^3$	$\leq 75 \times 10^9/\text{L}$ or $\geq 700 \times 10^9/\text{L}$
Leukocytes	$\leq 2,800/\text{mm}^3$ or $\geq 16,000/\text{mm}^3$	$\leq 2.8 \times 10^9/\text{L}$ or $\geq 16 \times 10^9/\text{L}$
Eosinophils	$\geq 10\%$	
Neutrophils	$\leq 15\%$	
Urinalysis		
Protein	Increase of ≥ 2 units	
Glucose	Increase of ≥ 2 units	
Casts	Increase of ≥ 2 units	

Abbreviations: BUN = blood urea nitrogen; LDH = Lactate dehydrogenase; SGOT (AST) = serum glutamic oxaloacetic transaminase (aspartate aminotransferase); SGPT (ALT) = serum glutamic pyruvic transaminase (alanine aminotransferase)

Vital Sign Values			
Variable	Criteria		Change Relative to Baseline
Heart Rate	≥ 120 bpm	and an	increase of ≥ 15 bpm
	≤ 50 bpm	and a	decrease of ≥ 15 bpm
Systolic Blood Pressure	≥ 180 mmHg	and an	increase of ≥ 20 mmHg
	≤ 90 mmHg	and a	decrease of ≥ 20 mmHg
Diastolic Blood Pressure	≥ 105 mmHg	and an	increase of ≥ 15 mmHg
	≤ 50 mmHg	and a	decrease of ≥ 15 mmHg
Weight			change of $\geq 7\%$ body weight

ECG Values		
ECG parameter	Low	High

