The percentage of subjects with specific treatment-emergent laboratory values (ie, lab values collected after the first dose in Stage 2 Period 5) that meet the PDLC criteria shown in [Table 8](#) by parameter will be summarized altogether (over the duration from first dose in Stage 2 Period 5 through Stages 3 and 4 to the DBL date), not by visit. The incidence rates of PDLCs will be presented. Unscheduled visits will be included in evaluating the PDLC summary.

A listing will be provided of subjects meeting the PDLC criteria. If a subject has at least 1 post-baseline value that meets the PDLC criteria for any lab parameter, then all values of that parameter for that subject will be listed. For the PDLCs, it is possible for subjects to appear in both categories for any parameter.

Table 8: Pre-defined Limits of Change Criteria for Clinical Safety Laboratory Data

Laboratory Test	Parameter for ANY Value and LAST Value
Chemistry	
Albumin	Composite: < LLN and > 25% decrease from BL
Bilirubin	Composite: > ULN and > 25% increase from BL
	Absolute Value: > 2X ULN
Bicarbonate	Absolute Value: < 16 mEq/L
Calcium	Composite: > ULN and > 10 % increase from BL
Phosphorus	Composite: < LLN and > 25% decrease from BL
	Composite: > ULN and > 25% increase from BL
Potassium	Composite: < LLN and > 15% decrease from BL
	Composite: > ULN and > 15% increase from BL
Sodium	Composite: < LLN and decrease > 5 mEq/L or more from BL
	Composite: > ULN and increase > 5 mEq/L or more from BL
Uric Acid	Male: absolute value \geq 624.6 mM
	Female: absolute value \geq 505.6 mM
	Composite: < LLN and > 25% decrease from BL
	Composite: > ULN and > 25% increase from BL
ALT	Absolute Value: > 3X ULN
	Absolute Value: > 5X ULN
	Absolute Value: > 8X ULN
AST	Absolute Value: > 3X ULN
	Absolute Value: > 5X ULN
	Absolute Value: > 8X ULN

Table 8: Pre-defined Limits of Change Criteria for Clinical Safety Laboratory Data (Continued)

Laboratory Test	Parameter for ANY Value and LAST Value
Chemistry (Continued)	
ALT > 3X ULN and Tbili > 2X ULN	Composite: ALT > 3X ULN and Tbili > 2X ULN (with the Tbili elevation > 2 X ULN within 30 days of the ALT elevation > 3X ULN)
AST > 3X ULN and Tbili > 2X ULN	Composite: AST > 3X ULN and Tbili > 2X ULN (with the Tbili elevation > 2X ULN within 30 days of the AST elevation > 3X ULN)
CK	Absolute CK \geq 2X ULN or 2X baseline value
Hematology	
Hemoglobin	Male: absolute value \leq 11.5 g/dL
	Female: absolute value \leq 9.5 g/dL
	Change: \geq 2 g/dL decrease from BL

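### SAP Table 8 counts stable or falling disease-related CK, ALT and AST elevations as treatment-emergent limit events and does not show who was already above the limit at baseline

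*SAP*

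**What the plan says.** SAP Section 10.4 summarises the percentage of subjects with "treatment-emergent laboratory values (ie, lab values collected after the first dose in Stage 2 Period 5") that meet the limits in Table 8. The count covers the whole period to database lock, is not by visit, and includes unscheduled visits. The table's column heading is "Parameter for ANY Value and LAST Value".

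- **ALT and AST:** each has three rows, starting at "Absolute Value: > 3X ULN" and rising to 5 and 8 times ULN. A further row for each pairs the enzyme with bilirubin, for example "Composite: ALT > 3X ULN and Tbili > 2X ULN". None mentions baseline.
- **CK:** one row, at or above "2X ULN or 2X baseline value".
- **Other analytes:** albumin, bilirubin, calcium, phosphorus, potassium, sodium, uric acid and platelets each have at least one row that also requires a change from baseline, such as "Composite: > ULN and > 25% increase from BL".

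Protocol Appendix 2 singles out "Safety laboratory analytes which are known to be elevated in some adults with Pompe disease (eg, AST, ALT, LDH"), together with analytes missing from its own table, which include CK. These are to be reviewed "based on the magnitude of the out of range value as compared to the normal range and the subject's baseline value", along with the investigator's coding.

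SAP Table 11 records that shift tables are no longer produced and that the pre-defined limits take their place. It adds that the new criteria are not identical to the protocol's.

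**The concern.** Table 8 is titled as limits of change, and its counts are labelled treatment-emergent. For the three enzymes that Pompe disease itself can raise, a subject can enter the count without any change. Protocol Section 6.4.2.6 reports that CK, ALT and AST improved on treatment, and SAP Section 10.5 analyses CK as a pharmacodynamic marker. One falling CK series can therefore appear both as a pharmacodynamic improvement and as a safety event.

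The study has no control arm, so no comparator rate shows the background level. Without shift tables, a reader of the incidence table cannot tell a new elevation from one present at entry, and a real new rise can sit unnoticed among elevations that were there from the start.

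**Working it through.** **Inputs.** The rules are those of SAP Table 8, with all values in multiples of ULN. Let b be the baseline value and p a post-dose value. The documents state no incidence for these limits and no baseline CK, ALT or AST distribution, so there is no plan figure to reproduce.

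**CK, literal reading.** Flag if p ≥ 2 or p ≥ 2b, which is p ≥ 2 × min(1, b).
- If b > 1, then 2b > 2, so the baseline limb never changes the result.
- If b < 1, the baseline limb lowers the threshold: 0.8 rising to 1.6 is flagged.
- For b ≥ 2, the flag survives any fall up to 1 − 2/b. For b = 3 this is 1 − 2/3 = 33%; for b = 4, 50%; for b = 6, 67%.
- Example: 3.0 × (1 − 0.30) = 2.1 ≥ 2, so it is flagged.

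**ALT and AST, lowest row.** Flag if p > 3. For b > 3, the flag survives any fall smaller than 1 − 3/b. For b = 4 this is 25%, so a 10% fall to 3.6 is flagged; for b = 6 it is 50%. The 5 and 8 × ULN rows work the same way. The bilirubin composites are less exposed, because a muscle-enzyme elevation alone does not meet them.

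**Who is not affected.** A subject with b < 2 (CK) or b ≤ 3 (ALT, AST) is not flagged when stable or falling, apart from visit-to-visit variation.

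**CK, second reading.** The row could instead mean 2 × ULN when baseline is normal and 2 × baseline when it is raised. A baseline of 3 would then be flagged only from 6 upwards, and the CK problem disappears.

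**Weight of one subject.** With 18 to 34 planned subjects, one subject is 1/34 = 2.9% to 1/18 = 5.6% of the total. In Cohort 3 (n = 5) it is 1/5 = 20%.

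**Illustration under assumed inputs.** The simulation used 100,000 subjects, 13 post-baseline visits, the any-value rule and log-normal values. Assumed between- and within-subject log SDs were 0.6 and 0.2 for CK, and 0.5 and 0.15 for ALT. The ranges run over assumed median baselines of 2 to 4 × ULN (CK) and 1.5 to 3 × ULN (ALT).

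| Rule | No true change | True 30% fall |
|---|---|---|
| CK, literal reading | 72.0% to 95.7% | 48.6% to 86.3% |
| CK, second reading | 4.6% to 5.8% | about 0.1% |
| ALT > 3 × ULN, all flagged | 19.1% to 68.9% | 5.7% to 41.9% |
| of which baseline ≤ 3 × ULN | 10.2% to 19.2% | 0.6% to 2.2% |

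With no true change, the flagged ALT subjects who were already above the limit make up 19.1 − 10.2 = 8.9% to 68.9 − 19.2 = 49.7% of all subjects. The width of these ranges shows that the size depends on baseline values the documents do not give.

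**Which baseline.** For Cohort 1, SAP Table 3 takes the safety baseline at Visit 9 (Visit 8 if missing). By then a subject has had six study infusions: three in Stage 1 and three in Period 4 (Protocol Table 8). SAP Section 10.5 sets the CK pharmacodynamic baseline at Visit 2. The CK row does not say which applies.

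**The case against.** The case for leaving Table 8 alone has real substance.

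- **The ALT and AST multiples are not arbitrary.** The stopping criteria in Protocol Section 8.5 use the same 3, 5 and 8 × ULN multiples and the bilirubin combination, also without a baseline term. Counting subjects who cross them is a legitimate display. This stands, and the rows should stay.
- **Appendix 2 is not a tabulation rule.** Its own table lists AST and ALT at 3 × ULN with no baseline term, and its narrative describes case review. This stands in part: the appendix shows that baseline matters for these analytes, but it does not dictate how Table 8 should count.
- **The change is disclosed.** Table 11 says the criteria differ and gives consistency with Study ATB200-03 as the reason. The SAP also states that it supersedes the protocol's methods. True, but Table 11 does not say that the categorical view of baseline against later values is lost for these enzymes.
- **Other displays show the direction of change.** Change and percent change from baseline are summarised, mean change is plotted for ALT, AST and CK, and every value of a flagged parameter is listed. These soften the harm but do not correct the incidence figure.
- **Tightening the rule would lose signal.** Requiring both CK limbs would miss a rise from 3 to 5.9 × ULN, since 5.9 < 2 × 3. Excluding subjects already over a limit would drop an ALT rise from 3.1 to 4.9 × ULN from every ALT row. In Cohort 1 it would also hide elevations that arose on the six infusions before Visit 9. This is decisive against either remedy.

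**Conclusion.** The concern holds in a limited form. As written, the ALT and AST rows have no baseline condition, and the CK row uses baseline only as an alternative trigger that does nothing above ULN. Subjects already over a limit are counted whether they worsen, stay level or improve, and nothing in the limits table separates them. The CK part rests on the literal reading; under the second reading the defect is ambiguous wording, which still has to be settled. The counts are descriptive, no hypothesis is tested, and the effect is confined to subjects above a limit at baseline. This is a worthwhile and cheap improvement to the safety tables, not a threat to the study's conclusions.

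Three stronger readings are tempting and should not be drawn.
- A reader might infer that all three limits ignore baseline. The CK row names it.
- A reader might infer that the counts mostly measure disease at entry. Appendix 2 says only that some adults have raised values, the documents give no baseline distribution, and the simulated percentages follow from assumptions.
- A reader might infer that the treatment-emergent label is misused. The SAP defines it openly as a matter of timing; the problem is what that definition leaves out of the table.

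**What to change.** 1. Keep the absolute ALT and AST rows and the bilirubin composites, and drop no subject from the counts.
2. For each of these limits, report separately the subjects who already met it at baseline and those who newly met it.
3. Replace the single CK row with two reported limbs: at or above 2 × ULN, also split by baseline status, and at or above 2 × baseline. This settles the ambiguity without requiring both.
4. Name the baseline in a table footnote. For Cohort 1, show status at the Visit 9 safety baseline and also at the last value before the first Stage 1 dose, so that elevations arising on earlier study doses stay visible. Protocol Table 9 schedules serum chemistry at Screening and Visit 3 but not at Visit 2, so the second value will come from the Visit 3 pre-dose sample or Screening.

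Newly met counts will still include some crossings from ordinary variation, and the footnote should say so. The cost is a few extra table rows and one derived flag. No new data are needed, and the ALT and AST totals remain available for comparison with Study ATB200-03.

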10.5. Pharmacodynamic Markers

Pharmacodynamic parameters (CK and urine Hex4) will be analyzed separately from the other safety lab parameters. The baseline for the PD parameters will be the original study baseline at Visit 2 (as defined in Section 6.4.1). The PD summaries for Stage 1 and for Stage 2 have been reported in iCSR-1 and will not be repeated in this SAP unless the underlying data have changed. Otherwise, the pertinent summaries will be copied from iCSR-1 into the final CSR.

The analysis of PD data collected during Stage 2 Period 5 through Stages 3 and 4 to the DBL date will be reported. Subjects with both baseline and at least 1 post-baseline assessment will be analyzed on the Efficacy population. Figures of the mean (\pm SE) absolute change from baseline will be plotted for CK and urine Hex4. The mean \pm SD values at baseline will be indicated in a legend for the plots. Additionally, all PD data will be presented in subject data listings.

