Subjects in Cohort 1 will participate in Screening, Baseline, Stage 1 (3-period, fixed-sequence, single-ascending dose of ATB200 alone), Stage 2 (2-period, fixed-sequence, multiple-dose of 20 mg/kg ATB200 co-administered with multiple-ascending doses of AT2221), and Stage 3 (a 24-month extension stage with continued dosing of 20 mg/kg ATB200 co-administered with 260 mg AT2221) of the study. Stage 4 treatment period will begin at the end of Stage 3 and continue as an open-label extension until subject withdrawal, regulatory approval or marketing authorization and/or commercialization in the participating subject's country, or study termination by Amicus.

Subjects in Cohorts 2, 3, and 4 will participate in Screening and Baseline for Stage 3 of the study, as well as Stage 3 dosing-visits. Additionally, subjects in Cohort 3 will participate in serial 24-hour PK visits. Subjects in Cohort 2 and 4 will not participate in PK analyses. The procedures and assessments performed are as follows:

Screening:

- At Screening for either Stage 1 or Stage 3, all subjects will provide informed consent and undergo review of eligibility criteria. Assessments for all subjects include medical history (including forced vital capacity [FVC] and 6MWT, CK, alanine aminotransferase [ALT], aspartate aminotransferase [AST], and urine Hex4 lab results) and history of falls; review of prior and concomitant medications and nondrug therapies; vital signs (heart rate [HR], respiration rate [RR], blood pressure [BP], and temperature); height; weight; comprehensive physical examination (PE); 12-lead electrocardiogram (ECG); clinical safety laboratory assessments (serum chemistry, hematology, and urinalysis); urine pregnancy test; and urine sample for Hex4. Blood samples will also be obtained for immunological assessments (total and neutralizing antibodies, exploratory pro-inflammatory cytokines/other biomarkers of immune system activation, cross-reactivity to alglucosidase alfa, and immunoglobulin E [IgE]), exploratory biomarkers of Pompe disease, and immunogenicity. For subjects in Cohorts 1, 2, and 4, a history of prior infusion-associated reactions (IARs) will also be obtained, and gene that encodes human acid α -glucosidase (*GAA*) genotyping will be performed for those who are unable to provide *GAA* genotyping report at screening. A subject who meets all of the inclusion criteria and none of the exclusion criteria will be assigned to Stage 1 as described above in [Table 1](#).

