10.2.11.1. Serum Chemistry

The serum chemistry parameters are described in [Table 16](#).

Table 16: Serum Chemistry Parameters

ALT	Creatinine
Alkaline phosphatase	Gamma-glutamyltransferase
AST	Glucose
Albumin	Lactate dehydrogenase (LDH)
Bilirubin, total	Magnesium
Blood urea nitrogen	Phosphorous
Calcium, total	Potassium
Carbon dioxide, total (bicarbonate)	Protein, total
Chloride	Sodium
Creatine phosphokinase (CK)	Uric acid

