6.4. Derived and Transformed Data

6.4.1. Baseline Definition

In general, baseline assessment is defined as the last non-missing result on or prior to the administration of the first dose of study medication. Baseline definitions for different variables during specific stages of the study are provided in [Table 3](#).

Table 3: Baseline Visit by Study Stage, Cohort, and Variable

Cohort	Assessment at Screening (V1, Days -28 to -1)	Assessment at Baseline (V2, Day 0)	Result Used as Baseline
Safety Data (including vital signs, laboratory data, ECG, PEs, etc) During Stages 1 and 2			
Cohort 1	X	X	Baseline is the last result obtained on/prior to V2; If result from V2 is unavailable, then use V1.
Note: Safety results for Stages 1 and 2 were reported in iCSR-1 and will not be repeated here.			
Safety Data During Stage 2 Period 5 and Stages 3 and 4			
Cohort 1	X	X	Baseline is the last result obtained on/prior to the start of the 20 mg/kg ATB200 + 260 mg AT2221 dose in Stage 2 Period 5. If the result from V9 is unavailable, then use V8. See Section 6.4.5 .
Cohorts 2, 3, and 4	X	X	Baseline is the last result obtained on/prior to V2. If result from V2 is unavailable, then use V1.
Efficacy Data, Biomarkers, and PROs During Stage 2 Period 5 and Stages 3 and 4			
Cohorts 1, 2, 3, and 4	NA	X	Baseline will be the result obtained at V2.

Abbreviations: ECG = electrocardiogram; NA = not applicable; PEs = physical examinations (which includes brief physical examination and comprehensive physical examination); PROs = patient-reported outcomes; V = visit

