6.4.5. Study Day (Relative Day)

The reference start day is defined for Cohort 1 and for Cohorts 2, 3, and 4 as follows:

- For Cohort 1: Visit 9 (Day 85 in Stage 2, Period 5) is considered the reference start day. This is the day of first dose of the 20 mg/kg ATB200 + 260 mg AT2221 co-administration.
- For Cohorts 2, 3, and 4: The study Day 1 in each cohort is the reference start day.

There will be no Day 0. If the date of interest occurs on or after the reference start day, then the relative study day is calculated as: $(\text{date of interest} - \text{date of reference start day} + 1)$.

Note: The appropriate reference start day should be used depending on whether the summary involves Cohort 1 or Cohorts 2, 3, and 4. For example, for Cohort 1, the relative day of the assessment at V12 will be calculated as: date of V12 – 85 + 1 (ie, Day 43).

If the date occurs before the reference start day, then study day is calculated as: $(\text{date of interest} - \text{date of reference start day})$. Thus, days before the reference start day will have a negative day displacement. For example, for Cohort 1, the relative day of the assessment at the efficacy baseline (V2) will be calculated as: date of baseline assessment – 85.

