^b Cohort 1 target day for Month X (starting from V9) is determined as (X * 30) + 43. For example, the target day for Month 3 is approximately at Day 3 * 30 + 43 = 133.

^c For safety analysis by visit, baseline is taken from Visit 9 (Day 85), but for efficacy, biomarker, and PRO analyses, baseline value is taken from Visit 2 (Day 1). See Section 6.4.1 and Section 6.4.5.

^d Tx is the target day of planned assessment visit at Month X.

- If the derivation starts from the original study day at V2, then: T_{MONTH X} = (30 * X + 127). For example, the target day at Month 54 = T_{MONTH 54} = 30 * 54 + 127 = 1747. Target day of the assessment visit immediately before Month X is given by T_{BEFORE}. For example, T_{BEFORE} = T₄₈ = (30 * 48 + 127) = 1567. Target day of the assessment visit immediately after Month X is given by T_{AFTER} = T₆₀ = (30 * 60 + 127) = 1927. The visit windows are then given as d1 – d2, where d1 = ([T_{BEFORE} + T_{MONTH X}] / 2) + 1 and d2 = (T_{MONTH X} + T_{AFTER}) / 2.
- If the derivation starts from Visit 9, then target day at Month X is given by T_{MONTH X} = (30 * X + 43). For example, the target day at Month 54 is T_{MONTH 54} = 30 * 54 + 43 = 1663. Target day of the assessment visit immediately before Month X is given by T_{BEFORE}. For example, T_{BEFORE} = T₄₈ = (30 * 48 + 43) = 1483. Target day of the assessment visit immediately after Month X is given by T_{AFTER} = T₆₀ = (30 * 60 + 43) = 1843. Visit windows are given as d3 – d4, where d3 = ([T_{BEFORE} + T_{MONTH X}] / 2) + 1 and d4 = (T_{MONTH X} + T_{AFTER}) / 2.

^e LAV represents the result obtained from the subject’s last visit of assessment. Summary at the LAV will only be provided for the efficacy analyses.

Efficacy data will be summarized at: Baseline (Visit 2), Visit 12, Month 3, Month 6, Month 9, Month 12, Month 15, Month 18, Month 21, Month 24, and every 6 months thereafter in Stage 4. Safety data will be summarized at: Baseline (Visit 9), Visit 10, Visit 11, Visit 12, Month 3, Month 6, Month 9, Month 12, Month 15, Month 18, Month 21, Month 24, and every 6 months thereafter in Stage 4.

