6.5.2. Visit Windows for Cohorts 2, 3, and 4 Data

For Cohorts 2, 3, and 4, the visit windows in [Table 5](#) will be used for analyses of safety and PD markers, and [Table 6](#) for the efficacy data.

Table 5: Visit Windows for Analyses of Cohorts 2, 3, and 4 Safety and Pharmacodynamic Data

Visit Name	Target Day	Visit Windows
Baseline	NA	Baseline is Visit 2
Day 1	1	Day 1 is Visit 3
Week 2	15	Day 2 – 22
Week 4	29	Day 23 – 60
Month 3	91	Day 61 – 136
Month 6	181	Day 137 – 226
Month 9	271	Day 227 – 316
Month 12	361	Day 317 – 406
Month 15	451	Day 407 – 496
Month 18	541	Day 497 – 586
Month 21	631	Day 587 – 676
Month 24	721	Day 677 – 811
Month 30	901	Day 812 – 991
Month 36	1081	Day 992 – 1171
Month 42	1261	Day 1172 – 1351
Month 48	1441	Day 1352 – 1531
Month 54	1621	Day 1532 – 1711
Month 60	1801	Day 1712 – 1891
Month X ^a	T _{MONTH X}	d1 – d2

Abbreviation: NA = not applicable

^a Target day of planned assessment visit at Month X is denoted T_{MONTH X} and it is given by T_{MONTH X} = (30 * X + 1). For example, the target day at Month 54 = T_{MONTH 54} = 30 * 54 + 1 = 1621. Target day of assessment visit immediately before Month X is given by T_{BEFORE}. For example, T_{BEFORE} = T₄₈ = (30 * 48 + 1) = 1441. Target day of assessment visit immediately after Month X is given by T_{AFTER}. For example, T_{AFTER} = T₆₀ = (30 * 60 + 1) = 1801. The visit windows are then given as d1 – d2, where d1 = ([T_{BEFORE} + T_{MONTH X}] / 2) + 1 and d2 = (T_{MONTH X} + T_{AFTER}) / 2.

Table 6: Visit Windows for Analyses of Cohorts 2, 3, and 4 Efficacy Data

Visit Name	Target Day	Visit Windows
Baseline	NA	NA (Baseline is Visit 2)
Month 3	91	Day 61 – 136
Month 6	181	Day 137 – 226
Month 9	271	Day 227 – 316
Month 12	361	Day 317 – 406
Month 15	451	Day 407 – 496
Month 18	541	Day 497 – 586
Month 21	631	Day 587 – 676
Month 24	721	Day 677 – 811
Month 30	901	Day 812 – 991
Month 36	1081	Day 992 – 1171
Month 42	1261	Day 11872 – 1351
Month 48	1441	Day 1352 – 1531
Month 54	1621	Day 1532 – 1711
Month 60	1801	Day 1712 – 1891
Month X ^a	T _{MONTH X}	d1 – d2
LAV	Target day corresponding to the LAV	Visit window corresponding to the LAV

Abbreviations: LAV = last assessed value; NA = not applicable

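### The SAP takes the CK and Hex4 baseline from Visit 2 with no fallback, but the protocol schedules neither marker at Visit 2 in any cohort

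*SAP*

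**What the plan says.** SAP 10.5 covers the two PD markers, CK and urinary Hex4, and says: "The baseline for the PD parameters will be the original study baseline at Visit 2", referring to 6.4.1. In 6.4.1, Table 3 puts biomarkers in one row with efficacy and PRO data for Cohorts 1 to 4. That row marks Screening as not applicable and Visit 2 as the source: "Baseline will be the result obtained at V2". The safety rows of the same table each name a substitute visit; this row does not. For Cohort 1, Table 4 footnote c says "for efficacy, biomarker, and PRO analyses, baseline value is taken from Visit 2 (Day 1"). For Cohorts 2 to 4, Table 5 sets baseline at Visit 2 and lists a separate row: "Day 1 is Visit 3".

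Section 6.4.1 opens with a different, general rule: "baseline assessment is defined as the last non-missing result on or prior to the administration of the first dose of study medication".

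On the protocol side, the synopsis lists at Screening "clinical safety laboratory assessments (serum chemistry, hematology, and urinalysis); urine pregnancy test; and urine sample for Hex4", and Table 16 includes "Creatine phosphokinase (CK") in serum chemistry. The synopsis list of Baseline Visit assessments has no chemistry or Hex4 sample.

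**The concern.** The visit that the SAP names as the PD baseline is one at which the protocol takes no PD sample. SAP 6.4.3 sets change and percent change to missing when the baseline is missing, and 10.5 analyses only subjects who have a baseline. Read literally, the planned change summaries, the mean-change figures and the baseline mean and SD in the figure legends cannot be produced from per-schedule samples.

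In practice a programmer will substitute something. The candidates are not equivalent: one is a result from the day of first dose, the other a Screening result up to about four weeks older. An unrecorded choice could make the final report differ from the second interim report, which analysed PD over the same period. It could also put two baselines into one report, because Stage 1 and 2 PD summaries are to be copied from the first interim report.

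**Working it through.** No figure in the plan needs reproducing. The check sets the SAP rule beside the protocol schedules and counts.

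**Step 1. Where the samples are scheduled.** Rows for serum chemistry (contains CK) and urine Hex4:

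| Protocol schedule | Screening | Baseline (Visit 2) | Visit 3 / Day 1 |
|---|---|---|---|
| Table 9, Cohort 1 | both | neither | both |
| Table 11, Cohort 2 | both | neither | both |
| Table 12, Cohort 3 | both | neither | both |
| Table 13, Cohort 4 | both | neither | both |

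Schedules with either marker at Visit 2: 0 of 4. Schedules with both markers at Screening and at Visit 3/Day 1: 4 of 4.

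**Step 2. Are the blank cells real?** Protocol 10.2.18 explicitly excludes the Baseline Visit from Hex4 collection, in a clause limited to Stages 1 and 2 and so to Cohort 1. For Cohorts 2 to 4 the evidence is the blank cells, supported by the synopsis lists. The pregnancy-test row has the same blank, and Protocol 10.2.17 confirms it in words.

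**Step 3. Consequence under the stated rule.** No Visit 2 result means no baseline, so change is missing (SAP 6.4.3) and the subject fails the 10.5 inclusion condition. Named windows affected:

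- Table 4: Visits 10, 11, 12 (3) + Months 3 to 24 every 3 months (8) + Months 30 to 60 every 6 months (6) = 17.
- Table 5: Day 1, Week 2, Week 4 (3) + 8 + 6 = 17, or 16 if Day 1 becomes the baseline.

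Both tables then continue to an open-ended Month X.

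**Step 4. How many subjects.** SAP Table 2 plans 11 + 4 + 5 + 6 = 26 to 11 + 6 + 5 + 8 = 30. With the protocol text's 10 to 12 for Cohort 1, the range is 10 + 4 + 5 + 6 = 25 to 12 + 6 + 5 + 8 = 31. The PD analysis uses the Efficacy population, so the number analysed can be smaller.

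**Step 5. What the general rule would give.** Each cohort has two scheduled candidates per marker, Screening and Visit 3/Day 1, against none under the Table 3 row. Protocol 10.2.11 places safety laboratory samples before dosing, so the Day 1 CK is a pre-dose value. Protocol 10.2.18 does not time Hex4 relative to dosing.

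**Step 6. Gap between the candidates.** Protocol 10.1.1 allows Screening up to 28 days before treatment. The Table 9 columns (Screening from Day -28, Visit 3 at Day 1 with a 3-day window) allow 28 + 1 = 29 days nominally and 29 + 3 = 32 with the window.

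**The case against.** **The SAP already has a fallback.** Section 10.5 points to 6.4.1, whose opening sentence is the rule one would want. But that sentence is offered as a general default, and Table 3 then defines baseline by variable. The specific row says Visit 2 and rules out Screening, and 10.5 repeats Visit 2.

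**Protocol 10.1.2 lets the Screening value stand in.** It is permissive only, and SAP 2 says the SAP's methods supersede the protocol's. The two rescues also disagree: the general rule selects the Day 1 pre-dose result, while 10.1.2 selects Screening.

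**Visit 2 is used loosely to mean the day of first dose.** This has some force for Cohort 1. Footnote c labels Visit 2 as Day 1, Protocol Table 9 has it as Day 0, and SAP 6.4.5 says "There will be no Day 0". The reading fails for Cohorts 2 to 4, where Table 5 separates the Baseline row from the Day 1 row.

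**Results will be produced anyway, and they are exploratory.** Protocol 6.4.2.6 reports CK and Hex4 improvement, so a baseline was used, and all PD values will be listed regardless. It stands that this is a defect in the written rule and not proof that results will be lost. Unscheduled Visit 2 samples may exist, and CK and Hex4 history is reviewed at the Baseline Visit, but those are historical values.

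**A Day 1 baseline gives CK two baselines in Cohorts 2 to 4.** This is a fair point. The safety row there falls back to Screening for per-schedule samples. The SAP already analyses PD CK apart from safety laboratory data, and in Cohort 1 the two baselines already differ (Visit 2 against Visit 9), but the difference should be stated.

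**Conclusion.** The concern holds. The PD baseline rule is wrong as written: it names a visit with no scheduled CK or Hex4 sample in any of the four schedules. For a subject sampled per protocol, change from baseline is missing at every window for both markers. This rests on the schedules having been followed; the number of unscheduled Visit 2 samples is not given. It also rests on the Table 3 row governing over the general sentence above it.

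The likely cause is that Table 3 groups biomarkers with function tests and PROs, which are collected at Visit 2 and not as Screening assessments; CK and Hex4 follow the reverse pattern.

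This should be fixed before database lock. The analyses are descriptive and no hypothesis test depends on them. But CK and Hex4 are the only PD endpoints in SAP 4.3, and CK change is a primary safety endpoint in Protocol 12.1.1.

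**What to change.** Before database lock:

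1. Replace the Visit 2 rule for CK and Hex4 with the general rule of SAP 6.4.1: the last non-missing result on or before the first dose of any study drug. This is the Visit 3/Day 1 pre-dose result, otherwise Screening.
2. Check recorded Hex4 collection times on Day 1, since the protocol does not fix them relative to dosing.
3. Align 10.5, the Table 3 biomarker row, Table 4 footnote c (including its Day 1 label for Visit 2) and Table 5. Where the Day 1 sample is the baseline, do not report Day 1 as a post-baseline window for these markers.
4. Compare the choice with the baseline used in the second interim report, and in the first for copied summaries, and disclose any difference.
5. State that the CK criterion in Table 8 based on twice baseline uses the safety baseline, if that is intended, and note that PD and safety CK baselines can differ.

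The cost is wording in four places, one cross-reference at Table 8, and two checks against existing records. No new samples are needed.
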